Overall Hypothesis: The Epharmix caregiver administered Rapid Cognitive Screen will have statistically significant correlation to the screen administered by a healthcare professional in the clinic.

Aim: Patient- Provider Communication -- To determine if the Epharmix EpxCogScreen can be used to obtain more timely clinical data about cognitive impairment for ongoing physician review, than by traditional methods.

Please save frequently

- c) **Describe the study design (e.g., outline the experimental procedures, describe the ethnographic observation and/or interviewing procedures, or outline survey research methods). Also, indicate if the subjects will be randomized in this study.**

Patients and their caregivers at Saint Louis University Geriatric Clinic will be included in this study and both must consent to participate in the study. The designated caregiver will enroll in the Epharmix program and will receive SMS text messages after one month. The messages will remind the caregiver of when to administer the Rapid Cognitive Screen and give them the option to receive all instructions via text or to use directions from a handout that the caregiver received while in clinic. All patient responses will be recorded through text and all patients will have been previously screened in the geriatric clinic by a health care professional. If the patient has an at-home RCS score decrease of three or more points, the patient's physician will be notified immediately through the Epharmix system and can then contact the patient for follow-up. Subjects will have the ability to opt out of the study electronically via text and phone at any point during the study. The scores of the screen from clinic and home administration will then

Protocol Title: EpxCogScreen

be analyzed to determine if a caregiver administered Rapid Cognitive Screen has high correlation to the screen administered in the clinic. A decrease in the baseline clinic score of three or more points will send an alert to the physician so that they can further evaluate the patient.

The clinic scores will be compared to the at-home RCS scores to determine the correlation coefficient between the two. In addition, at home scores will be compared to clinical diagnoses of dementia obtained from chart review. This will determine the validity of EpxCogScreen use in the geriatric population.

3. Study Procedures

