- a) Does this study involve conduct of research at multiple sites and the SLU PI is the direct recipient of a federal grant for this research? If yes, please complete and attach the Supplemental Application for Coordinating Center Activities. N

Page numbers from a grant may be referenced in 3b and 3c.

- b) Describe all study procedures; from recruitment through end-of-study, that the human subject must undergo in the research project. Please note: The box below is for text only. If you would like to add tables, charts, etc., attach those files in the Attachment section (#12).

Patients will be screened with the Rapid Cognitive Screen (RCS) in clinic as a part of the normal standard of care. Patients and caregivers will receive information about the study and a handout with instructions in the physicians office and can consent if they are interested in participating. If they enroll in the study, the caregiver will receive text message instructions for the RCS one month later. The caregiver can choose to administer the screen with instructions only via text or by using the handout received in the office. He/she will read the instructions to the patient and record responses via text message. The screen will take no more than 15 minutes to complete.

After the data is compiled from the at-home screen, a medical record review will occur. This will look at previously diagnosed medical conditions, which have been indicated in the "Epharmix Data Collection Sheet" in Section 12, and will compare this data to scores received on the RCS screens.

- c) Describe how data analysis will be performed (statistical tests, methods for evaluating data) and indicate the smallest group/unit for which separate reporting will occur. For studies involving a questionnaire, if data and reliability information are available, please describe or provide references. For full board, unfunded studies describe sample size determination and power analysis. If none, please justify.

Data analysis will occur between the patient's at-home and in-clinic RCS scores. The scores will be plotted against one another to determine the correlation between them. The total score correlation, along with the correlation for each individual component of the screen (free recall, clock-drawing, and insight). In addition, the sensitivity and specificity of the at-home screen will be determined based upon clinical diagnoses of patients based on chart review.

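### A handout from which the home screen can be given goes to patients as well as caregivers about a month or more before testing, and nothing in the protocol keeps any test items from the patient

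*Protocol*

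**What the plan says.** Protocol, Section 3b (study procedures): "Patients and caregivers will receive information about the study and a handout with instructions in the physicians office", after which they may consent. Then: "If they enroll in the study, the caregiver will receive text message instructions for the RCS one month later". On how the screen is given: "The caregiver can choose to administer the screen with instructions only via text or by using the handout received in the office", and "He/she will read the instructions to the patient and record responses via text message".

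Protocol, Section 2c (study design): the text messages "give them the option to receive all instructions via text or to use directions from a handout that the caregiver received while in clinic". Here only the caregiver is named as having received the handout. The alert rule in the same section reads: "If the patient has an at-home RCS score decrease of three or more points", the physician is notified.

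Other sections that bear on the point:
- Section 4g allows consent by telephone after the visit, so the handout can be held for longer than a month.
- Section 4h requires every patient to have had the RCS in clinic already.
- Section 3c analyses the clinic-home correlation for the total score and for each component, free recall among them. It also plans sensitivity and specificity of the home screen against chart diagnoses.
- Section 4a sets 100 patients and 100 caregivers.

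**The concern.** A cognitive screen with a free-recall component assumes that the patient meets the material at the moment of testing. If the handout carries the items, and the patient holds or reads it in the weeks beforehand, the home score partly measures preparation. Section 1a says that higher scores mean less impairment, so any gain makes patients look better at home.

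Two uses of the home score would suffer. At any fixed cut-off fewer patients would screen positive, so sensitivity would fall and specificity would rise. A true decline from the clinic score would also be partly cancelled, so some drops that should trigger the alert would not. The main hypothesis in Section 2b rests on correlation, which responds little to a shift in level.

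This is a matter of study conduct. An analysis plan cannot remove early exposure once it has happened.

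**Working it through.** **Reading the sections together.**
1. Recipient: Section 3b names patients and caregivers; Section 2c names the caregiver. The two are compatible (one handout per pair would satisfy both), but neither settles whether the patient holds or sees it.
2. Interval: the handout is given at the clinic visit and the prompt comes one month after enrolment. That is about one month with same-day enrolment and more with later consent.
3. Content: the handout can stand in for the full text instructions, and the screen can be given from it. It may therefore print items. It is an attachment that is not shown, so this cannot be confirmed.
4. Safeguard: no section says that items are kept from the patient until testing.

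**Illustration of size.** The protocol gives no score range, SD, share exposed or gain, and there is no figure of its own to reproduce. Everything here except the 100 pairs and the three-point rule is assumed.

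- True score ~ Normal(6.5, SD 2.0 to 2.5).
- Clinic = true + error.
- Home = true − decline + gain + error.
- Errors are independent with a common SD of 0.8 to 1.6.
- Observed scores are rounded and clipped to 0–10.
- Exposed pairs are chosen at random.
- There are 1,000,000 simulated pairs per setting.
- Settings (true SD, error SD): (2.5, 0.8), (2.5, 1.2), (2.0, 1.2), (2.5, 1.6).
- Detection is the chance of an observed drop of three or more, given a true decline of 3 and a clinic score of at least 3. It uses the Section 2c wording of the alert; Section 5d words the threshold differently.

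With no gain, r in the four settings is 0.890, 0.793, 0.717 and 0.689. Ranges over the four settings:

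| Exposed, gain | Rise in mean home − clinic | Fall in r | Detection |
|---|---|---|---|
| None | 0 | 0 | 0.585–0.645 |
| Half, 1 point | 0.42–0.45 | 0.013–0.019 | 0.481–0.498 |
| Half, 2 points | 0.79–0.85 | 0.046–0.070 | 0.368–0.413 |
| All, 1 point | 0.83–0.90 | 0.006–0.007 | 0.318–0.405 |
| All, 2 points | 1.58–1.70 | 0.023–0.028 | 0.092–0.242 |

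With only 10% exposed and a 1-point gain, detection falls by about 0.02–0.03 (0.604 to 0.581 in the second setting) and r by about 0.004–0.006. The 35–42% of declines missed with no gain come from the assumed measurement error, not from the handout.

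**Could the correlation show it?** Fisher interval for r = 0.79, n = 100:
- atanh(0.79) = 1.071 and SE = 1/√97 = 0.1015, so the half-width is 1.96 × 0.1015 = 0.199.
- The limits are tanh(0.872) = 0.70 and tanh(1.270) = 0.85.

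All the modelled falls stay inside the corresponding interval except one. From r = 0.890 (interval 0.84–0.92), a 2-point gain in half the pairs gives 0.820, just below the lower limit. Even there the trial has no reference r without early sight, so a value of 0.82 would simply be read as the result.

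**The case against.** The strongest case against is that the harm needs three steps, none of which the protocol states: the handout prints items, patients read them, and they still benefit a month later. Directions can explain how to give the screen and text back answers without listing recall content. The wording in Section 3b also fits one packet per pair in the caregiver's hands. Every patient has already met the screen in clinic, so some prior exposure exists whatever is done. The 50% and 100% exposure scenarios are assumptions; at 10% the effect is small.

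Most of this stands, and it sets the weight of the point. It does not remove it. The clinic exposure is part of the design, whereas early sight through the handout would be additional and avoidable.

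Three stronger readings are tempting, and the documents do not support them:
- A reader might infer that items are being leaked to patients. The handout is not shown, so this is a possibility only.
- A reader might infer that Sections 2c and 3b contradict each other. They are compatible; they merely leave the patient's access open.
- A reader might infer that the instruction mode, text or handout, must be recorded as a remedy. Mode is not exposure: the handout is given before any mode is chosen, so a patient tested by text may have seen it too. The choice is offered through the messages and may already be logged.

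**Conclusion.** The point holds as a minor one, to be considered, with low to medium confidence. As written, Section 3b lets the patient receive, about a month or more ahead, a handout from which the home screen can be given, and no section restricts access to any test items in it. Whether this biases anything depends on the handout's content.

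If items are printed and read, home scores could rise by an unknown amount, with lower sensitivity, higher specificity and masked drops. In the illustration, detection of a true 3-point decline falls from 0.585–0.645 to anywhere between a loss of 0.02–0.03 (10% gain 1 point) and 0.092–0.242 (all gain 2 points). These figures depend wholly on the assumed scale, SDs, exposure and gain, and are not estimates for this trial. With 100 pairs and no unexposed reference, the correlation would not reliably reveal the problem, whether the gain is uniform or uneven.

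**What to change.** Change Section 3b to agree with Section 2c: any material containing test items goes to the caregiver only, either sealed until testing or released with the one-month prompt. Directions that contain no items can stay open to both parties from the clinic visit. If the existing handout has no items, one sentence saying so settles the matter.

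The cost is a reissued or sealed handout, and caregivers can no longer read the item-bearing part in advance. The safeguard relies on caregiver compliance, and the retest effect of the clinic screen remains. It should be settled before enrolment, because early exposure cannot be corrected in the analysis.

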In 2011, the Affordable Care Act added routine cognitive screening as a component of the Medicare Annual Wellness Visit, but did not recommend a universal screening tool [2]. This initiative was supported by many public organizations, including the Alzheimer's Association. Typical neuropsychometric tests such as the Mini-Mental State Exam (MMSE) are administered in the physician's office and can take 7 to 15 minutes to complete [3]. This addition to the wellness visits demonstrates the increasing value of early diagnosis for Alzheimer's and other dementias. However, time constraints during patient visits may cause the physician to forgo a thorough cognitive screen. Unlike the MMSE, the Rapid Cognitive Screen (RCS) is a 3 item screening tool that takes less than 5 minutes to complete. This screen has exhibited

Protocol Title: EpxCogScreen

screening tool that takes less than 5 minutes to complete. This screen has exhibited remarkable sensitivity and specificity in detecting both mild cognitive impairment (sensitivity=0.87, specificity=0.70) and dementia (sensitivity=0.89, specificity=0.94) in patients over the age of 65 [4]. In addition, higher scores (less impaired) on the screen are indicative of lower rates of mortality. Due to the simplicity of this screening tool, it can be transformed into an at-home, telemedicine screen that would eliminate the time constraints that serve as a barrier to early detection.

While the U.S. Preventative Services Task Force (USPSTF) does not currently recommend frequent cognitive screening, there is very little evidence of potential risks from early screening and diagnoses [5]. Cognitive screens are meant to increase awareness of a patient's neurocognitive changes, not to diagnose. A formal diagnosis can only be completed after a physical exam of the patient, including neurological and psychiatric evaluations and lab tests by a geriatrician or neurologist, which decreases the likelihood of false positives.

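### Accuracy against chart diagnoses is planned for the home screen only; reporting the clinic RCS beside it in the same patients would give the home figures a benchmark within the study

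*Protocol*

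**What the plan says.** Two analyses bear on validity.

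- **Home against clinic.** Section 3c opens with "Data analysis will occur between the patient's at-home and in-clinic RCS scores": the scores are plotted against each other and correlated, in total and by component. The overall hypothesis in 2b is also a correlation between the two.
- **Home against chart.** Section 3c continues: "In addition, the sensitivity and specificity of the at-home screen will be determined based upon clinical diagnoses of patients based on chart review". Section 2c says the same: "at home scores will be compared to clinical diagnoses of dementia obtained from chart review". Neither sentence names the clinic screen.

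After setting out both analyses, 2c concludes: "This will determine the validity of EpxCogScreen use in the geriatric population".

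The clinic score exists for everyone. Section 2c states that "all patients will have been previously screened in the geriatric clinic by a health care professional", and a previous clinic RCS is an inclusion criterion in 4h. Section 3b says that the record review covers diagnosed conditions and "will compare this data to scores received on the RCS screens". The plural may include the clinic screen, but the sentence names no accuracy measure.

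Published RCS accuracy appears in 1a as background: "dementia (sensitivity=0.89, specificity=0.94) in patients over the age of 65", next to a pair for mild cognitive impairment (0.87 and 0.70).

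**The concern.** The study asks whether the RCS keeps its validity when a caregiver gives it at home instead of a professional in clinic. A home sensitivity and specificity against the chart mix three things: the effect of home administration, the case mix of this clinic, and errors in the chart diagnoses. The clinic RCS of the same patients, set against the same diagnoses, shares the last two to a large extent, so it is the natural yardstick for the first.

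The planned correlation does not supply that yardstick. It shows whether patients keep their relative position, not whether home scores sit higher or lower as a whole, and a shift of that kind changes who falls below a cut score. A low home specificity could then be blamed on the caregiver when the chart is at fault. A real loss could equally be excused as chart error.

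**Working it through.** The plan gives no accuracy target, prevalence or power to reproduce. Section 4a gives only 100 patients and 100 caregivers. The checks below are illustrations, with assumptions marked.

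**1. Correlation and a systematic shift.** Inputs: sensitivity 0.89 and specificity 0.94 (section 1a), used as a starting point for the clinic screen. Assumed: normal scores with equal spread in both groups, and home score = clinic score minus s standard deviations, so the correlation is exactly 1.

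- Home sensitivity = Φ(z(0.89) + s) = Φ(1.2265 + s)
- Home specificity = Φ(z(0.94) − s) = Φ(1.5548 − s)

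| s | correlation | sensitivity | specificity |
|---|---|---|---|
| 0 | 1 | 0.890 | 0.940 |
| 0.5 | 1 | 0.958 | 0.854 |
| 1.0 | 1 | 0.987 | 0.710 |

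**2. Chart error.** Inputs: 29% and 76% undiagnosed (section 1a, stated for Alzheimer's disease and applied here to dementia as an assumption). Prevalence: 1 in 9 is the figure in 1a for people over 65; 30% and 50% are assumed for a geriatric clinic. Missed cases are assumed to be independent of the screen result. With prevalence p and missed fraction m:

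apparent specificity = [(1 − p) × 0.94 + p × m × (1 − 0.89)] / [(1 − p) + p × m]

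For p = 0.30 and m = 0.29: (0.70 × 0.94 + 0.087 × 0.11) / 0.787 = 0.848.

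| missed | p = 1/9 | p = 0.30 | p = 0.50 |
|---|---|---|---|
| 29% | 0.911 | 0.848 | 0.753 |
| 76% | 0.868 | 0.736 | 0.582 |

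Under this independence assumption sensitivity is unchanged, so the ambiguity from missed diagnoses lies in specificity.

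**3. The two explanations side by side.** No home effect with 29% missed at 30% prevalence gives a home specificity of 0.848. A perfect chart with a home shift of 0.5 SD gives 0.854. The home figure cannot separate them.

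**4. What pairing adds.** Take both at once: a 0.5 SD shift, with 29% missed at 30% prevalence.

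- Clinic: 0.848, as above.
- Home: (0.70 × 0.854 + 0.087 × 0.042) / 0.787 = 0.764.
- Apparent loss: 0.848 − 0.764 = 0.084. True loss: 0.940 − 0.854 = 0.086.

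The difference survives the chart error almost intact, but only if missed diagnoses are unrelated to either screen.

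**5. Precision.** Assumed sensitivities: 0.89 in clinic and 0.75 at home. The half-width of the paired 95% interval is 1.96 × √{[p10 + p01 − (p10 − p01)²] / n}, where n is the number of diagnosed patients. Discordant probabilities (p10, p01) are either (0.16, 0.02), with the two screens strongly dependent, or (0.2225, 0.0825), with them independent. For n = 30 with the first pair: 1.96 × √(0.1604/30) = 0.143.

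| diagnosed patients | half-width | exact McNemar power (simulated) |
|---|---|---|
| 11 | 0.237 to 0.316 | 0 to 1% |
| 30 | 0.143 to 0.191 | 18 to 23% |
| 50 | 0.111 to 0.148 | 36 to 56% |

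The home-only figure is imprecise too. Exact 95% intervals for sensitivity are 0.587 to 0.998 for 10/11, 0.735 to 0.979 for 27/30, and 0.757 to 0.955 for 44/50.

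**The case against.** The strongest reply is that the plan already compares home with clinic within patients. That is the hypothesis and the first analysis in 3c; accuracy comes second. This stands. A reader might infer that the published pair in 1a is the only benchmark, or that home accuracy will be judged against it. The documents support neither: the published figures are background, and no section plans that comparison. Nor does 2c rest validity on the home accuracy figure alone, since its concluding sentence follows both analyses. What remains is narrower: the within-patient comparison is a correlation, so there is no within-study benchmark for accuracy. The planned scatter plot might show a shift to the eye, but the stated result is the coefficient.

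A second reply is that this is an omission that an analysis plan could fill, and that the plural in 3b may already cover the clinic screen. Nothing in 3c forbids the extra table. But the protocol does specify the accuracy analysis, twice, for the home screen, and 3b names no accuracy measure. The three sections should say the same thing.

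The third reply concerns the remedy. The clinic RCS is standard care and may have contributed to some diagnoses, which would favour the clinic score; the documents do not say whether it did. The home screen comes one month later, and the caregiver chooses text or handout instructions. The paired difference therefore does not isolate caregiver administration, and with 100 patients it will be imprecise. All of this stands. It limits the weight the difference can carry, but it does not make the home figure alone easier to interpret.

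**Conclusion.** The point holds as a specific, inexpensive improvement, not as a flaw that defeats the study. Accuracy is specified for the home screen only, while the same patients' clinic scores are used only for a measure that does not detect systematic shift. On the protocol's lower under-diagnosis figure, chart error alone moves an apparent specificity from 0.94 to between 0.75 and 0.91 over prevalences of 50% down to 1 in 9. A home shift of half a standard deviation falls within that range. These sizes rest on the assumed prevalences, the normal model, missed diagnoses independent of the screen, and the published accuracy as a starting value.

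It would go too far to conclude that a paired accuracy difference should replace the correlation as the test of validity, or that it would divide a shortfall cleanly between home administration and the chart. The likely interval widths, possible use of the clinic RCS in diagnosis, and the one-month gap rule that out.

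**What to change.** In 3c, with 2c and 3b brought into line, add text to this effect:

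> Sensitivity and specificity of the clinic RCS will be computed against the same chart diagnoses, in the same patients and at the same cut score as for the home screen. They will be reported beside the home figures, with paired home-minus-clinic differences and 95% confidence intervals, as a supporting estimate next to the correlation analysis.

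State the limits in the same place: the difference is not a powered test or the sole criterion of validity; intervals will be wide with 100 patients; the clinic RCS may have contributed to some diagnoses, which would favour the clinic score; and the screens are one month apart, so shared errors cancel only in part. Section 3b should say whether its comparison covers both screens.

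The cost is a few sentences and one extra table from data already collected. The downside is that the paired result may be imprecise, or look less favourable than the home figure alone.

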***** Subject Population(a-g) *****

4. Subject Population - In the space below, please detail the participants that you are requesting to recruit (include description of each group requested).

a) Number of evaluable subjects to be accrued.

200 (100 patients and 100 caregivers)

Exceeding the number listed here is a protocol violation. Prior IRB approval is required if additional participants are to be accrued. If applicable, this number should be consistent with your power analysis described in 3b.

b) What is the expected age range of subjects? (For example: ≥ 18 yrs to 90 yrs).

Patients must be over the age of 65 to participate. Caregivers can be greater than 18 years old to 90.
--

c) Requested Participant Description (e.g., gender, ethnicity, socio economic status, etc.). Include description of each group requested.

The population used will include all genders, socioeconomic, and ethnic backgrounds. Both patients with and without diagnoses of dementia will be included in the study.
--

d) If including vulnerable populations (minors, pregnant women and fetuses, <a href=<https://www.slu.edu/Documents/research/IRB/Neonates.docx> target=_blank>neonates, non-English speaking, economically or educationally disadvantaged, prisoners, adults temporarily or permanently unable to consent for themselves): 1) provide the rationale for the importance of including this population in the research, and 2) specify the measures being taken to minimize risks to potentially vulnerable subjects. Click on hyperlinks to access <a href=<https://www.slu.edu/division-of-research-administration-home/institutional-review-board->

Protocol Title: EpxCogScreen

(irb)/general-guidelines target=_blank>SLU Guidelines containing additional considerations and strategies for mitigating risks.

Any patient that visits the geriatric clinic at SLU and is over the age of 65 is eligible to participate in the study. Cognitive impairment and dementia are prevalent in this population, and early diagnosis is important to allow for patients to plan for their futures and have early intervention in the disease. Screening tools are used for early diagnosis, and this study would determine if an at home dementia screen could be used in the general geriatric population for earlier detection of disease.

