***** Benefits/Alternatives, Procedures to Maintain Confidentiality and Privacy *****

6. Benefits/Alternatives

a) **Benefits.** Describe the potential benefit(s) to be gained by the subjects and how the results of the study may benefit future subjects and/or society in general. Indicate if there is no direct benefit to the participants.

A potential benefit to the participants of the study would be earlier detection of cognitive decline since the patients would be screened in between physician visits. Earlier detection could lead to earlier treatment and more time to plan for the future. However, there may be no direct benefit to patients.

If it is determined that the intervention is a valid screening tool to be administered by caregivers, any patient over the age of 65 would be eligible to be screened. Earlier detection of dementia and cognitive decline could lead to earlier treatment and better management of the disease.

Protocol Title: EpxCogScreen

decline could lead to earlier treatment and better management of the disease.

- b) **Alternatives.** Describe any alternatives available to the subjects should they choose not to participate in the study. If no such alternatives exist, please state that the alternative is nonparticipation. For some studies, such as record reviews, a description of alternatives would not be applicable.

There are no alternatives available to the patient if they choose not to participate. The alternative is nonparticipation.

7. Procedures to Maintain Confidentiality and Privacy

Federal regulations require that research materials be kept for a minimum of three (3) years, and HIPAA documents be kept for a minimum of six (6) years after the closure of the study. For FDA-regulated projects, the PI may be required to keep the data and documents for a longer time period.

Confidentiality

To determine whether adequate provisions for confidentiality of data are in place, the IRB must ensure that research materials are stored in appropriate locations throughout the study (during collection, transport/transmission, analysis and long term storage). Research information must be protected using appropriate safeguards based on identifiability of the data and risk associated with the study (See SLU IRB Confidentiality Guidelines).

For the questions below, please use the following definitions:

Anonymous/De-identified: data contain no identifiers, including code numbers that investigators can link to individual identities;

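### Sensitivity and specificity of the home screen rest on charted diagnosis alone, so undiagnosed dementia counts as disease-free and this comparison cannot support a claim of earlier detection

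*Protocol*

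**What the plan says.** Protocol section 3c gives the accuracy analysis in one sentence: "the sensitivity and specificity of the at-home screen will be determined based upon clinical diagnoses of patients based on chart review". Section 2c announces the same comparison: "In addition, at home scores will be compared to clinical diagnoses of dementia obtained from chart review". Section 3b gives the timing and content of the review: "After the data is compiled from the at-home screen, a medical record review will occur", and "This will look at previously diagnosed medical conditions". No study procedure assesses patients whose charts hold no diagnosis.

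Section 1a sets a demanding standard for a diagnosis: "A formal diagnosis can only be completed after a physical exam of the patient, including neurological and psychiatric evaluations and lab tests". It also puts the undiagnosed share of Alzheimer's patients at 29% to 76%.

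Three statements draw on the results. Section 2c, after describing both the home-clinic comparison and the chart comparison, concludes: "This will determine the validity of EpxCogScreen use in the geriatric population". Section 4d says that "this study would determine if an at home dementia screen could be used in the general geriatric population for earlier detection of disease". Section 6a adds that, if the tool proves valid, "any patient over the age of 65 would be eligible to be screened".

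**The concern.** By the protocol's own account of what a diagnosis requires, and of how often one is missed, a chart without a diagnosis does not show that dementia is absent. Yet every chart-negative patient enters the specificity denominator as disease-free. A home screen that correctly finds an undiagnosed case is charged with a false positive. One that misses the case is credited with a true negative. Sensitivity is computed only in patients whose disease was already recognised.

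Earlier detection concerns exactly the undiagnosed cases. A comparison that counts them as non-cases cannot show whether the home screen finds them. At stake are the statement in 4d and any reading of the validity sentence in 2c as an unqualified statement of diagnostic accuracy.

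**Working it through.** The protocol states no target or expected accuracy for the home screen, so there is no planned figure to reproduce. The check asks what the charted reference would return if the home screen performed as the protocol reports for the Rapid Cognitive Screen (RCS).

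**Inputs from the protocol**
- Prevalence of 1 in 9 over age 65 (section 1a; general population, not this clinic).
- RCS sensitivity 0.89 and specificity 0.94 for dementia (section 1a; not the home version).
- 100 patients (section 4a).
- Under-diagnosed share f = 0.29, the lower end of the range in section 1a. It is an Alzheimer's figure, applied to dementia here as an assumption.

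**Assumed, not in the documents**
- f = 0.10.
- Positivity s = 0.50 in undiagnosed cases. The alternative s = 0.89 means that missed diagnosis is independent of the screen result.
- Charted diagnoses are correct, and sensitivity in charted cases is 0.89.

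**Formulas, per 100 patients**
- Cases P = 100/9 = 11.1; non-cases N = 88.9; undiagnosed cases u = P × f.
- Apparent specificity = (0.94 N + (1 − s) u) / (N + u).
- Sensitivity in all cases = 0.89 (1 − f) + s f.
- Standard error (SE) of specificity = √(0.94 × 0.06 / (N + u)).
- SE of sensitivity = √(0.89 × 0.11 / (P − u)).

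With f = 0 these return 0.94 and 0.89, as they should.

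**f = 0.10**: u = 1.1, charted cases 10.0, chart-negative patients 90.0.
- s = 0.89: specificity = (83.56 + 0.12) / 90.0 = 0.930.
- s = 0.50: specificity = (83.56 + 0.56) / 90.0 = 0.935.
- SE of specificity = √(0.0564 / 90.0) = 0.025.
- Sensitivity in all cases at s = 0.50: 0.801 + 0.050 = 0.851.
- SE of sensitivity = √(0.0979 / 10.0) = 0.10.

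**f = 0.29**: u = 3.2, charted cases 7.9, chart-negative patients 92.1.
- s = 0.89: specificity = (83.56 + 0.35) / 92.1 = 0.911.
- s = 0.50: specificity = (83.56 + 1.61) / 92.1 = 0.925.
- SE of specificity = √(0.0564 / 92.1) = 0.025.
- Sensitivity in all cases at s = 0.50: 0.632 + 0.145 = 0.777.
- SE of sensitivity = √(0.0979 / 7.9) = 0.11.

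**Direction.** Specificity is biased downward only if s exceeds 1 − 0.94 = 0.06. At s = 0.06 that bias vanishes, but sensitivity in all cases falls to 0.801 + 0.006 = 0.81 (f = 0.10) or 0.632 + 0.017 = 0.65 (f = 0.29). At s = 0.89 the reverse holds: sensitivity is right and specificity carries the error. As one error shrinks, the other grows.

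**Higher prevalence.** At an assumed 25% (P = 25, N = 75), specificity reads 0.913 (s = 0.89) or 0.926 (s = 0.50) at f = 0.10, and 0.867 or 0.901 at f = 0.29, with SE 0.026 to 0.027.

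**The case against.** The chart comparison is secondary. The only stated hypothesis is correlation between home and clinic scores, which needs no disease reference. The lay summary in section 2a links validity to that correlation, and the validity sentence in 2c follows both comparisons. A reader might infer that the missing reference assessment undermines the whole study. The documents do not support that: the main hypothesis can be tested as planned.

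A reader might also take the 29% to 76% range as this clinic's under-diagnosis rate and conclude that the bias is large. Nor is that supported. Section 1a attributes under-diagnosis to screening not being standard practice, whereas section 3b makes the clinic RCS standard of care and section 4h requires it before entry. If clinic positives are worked up (an assumption), a sensitivity of 0.89 implies about 11% missed, close to the 10% case. At prevalence 1 in 9 the specificity shift is then 0.005 to 0.010, under half a standard error. The sensitivity gaps at s = 0.50 (0.04 and 0.11) are within about one standard error on 8 to 10 charted cases.

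The text does not say before what date a condition must have been diagnosed, and the review follows the home data. That alone does not show that extraction is unblinded or undated: the data collection sheet attached in Section 12 is not shown, and an analysis plan could settle it.

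These arguments limit the weight of the point. They do not alter the stated reference, or the fact that section 4d claims what this comparison cannot show.

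**Conclusion.** The point holds as a cheap improvement to a secondary analysis. Followed as written, section 3c estimates agreement with charted diagnosis, not accuracy for dementia. It cannot support the earlier-detection statement in 4d, or an unqualified accuracy reading of the validity sentence in 2c. More patients would reduce the standard errors but not the bias.

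The size cannot be fixed from the documents. On the inputs above, the specificity error is 0.005 to 0.029 at prevalence 1 in 9, at most about one standard error, and larger if the clinic's prevalence is higher. The sensitivity error runs from none to 0.11 for s between 0.89 and 0.50, and is larger if undiagnosed cases rarely screen positive. These figures rest on a general-population prevalence, RCS performance carried over to the home version, and assumed values for under-diagnosis and positivity.

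**What to change.** 1. In 3c, name the result as sensitivity and specificity against charted diagnosis.
2. In 2c and 4d, limit the conclusion to agreement with clinic administration and with charted diagnosis, and drop earlier detection as something this study would determine.
3. In 3b, have chart diagnoses extracted without knowledge of the home score. Use diagnoses dated before the home RCS as the main reference, and count and report later, alert-prompted diagnoses separately. The alert to the physician is unaffected.
4. Optionally, here or in the analysis plan, tabulate both estimates over a stated range of under-diagnosis (for example 0 to 29%, with 76% as an outer bound) and of positivity in undiagnosed cases (for example 0.06, 0.50 and 0.89).

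The cost is some rewording, a blinded extraction and, if adopted, one small table; no new patients or tests are needed. The claim becomes more modest and the analysis slightly longer. The main reference also leaves out cases first found through a home alert, although the home screen found them correctly. That is accepted because patients with an alert would be evaluated when others are not, which would make verification depend on the test result; it is also why those cases are reported separately. The steps disclose and bound the bias but do not remove it, since chart-negative patients still receive no reference assessment.
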